#### Study Drug:

Phase 2 part: HBM9161

-Dose: Group 1: 340 mg; Group 2: 680 mg

- Method and route(s) of administration: The drug will be administered by subcutaneous injection once a week and 4 times per cycle. The number of treatment cycles will be as clinically indicated, with no more than 3 cycles per subject in the overall trial.

Phase 3 part: HBM9161

- Dose: to be determined (based on data from phase 2 part)

- Method and route(s) of administration: The drug will be administered by subcutaneous injection once a week, 4 times per cycle. The number of treatment cycles will be as clinically indicated, with no more than 3 cycles per subject in the overall trial.

Rescue treatment:

- Rescue treatment will be allowed during this study, including an increase in the dose or frequency of existing ITP concomitant drugs, and the addition of intravenous gamma globulin, anti-D immunoglobulin, high-dose glucocorticoid pulse, recombinant human thrombopoietin (rhTPO) or thrombopoietin receptor agonists, vinblastine, platelet transfusion, and plasmapheresis. The use of rescue treatment is based on the investigator's medical judgement and can be referred to the Expert Consensus on the Diagnosis and Treatment of Primary Immune Thrombocytopenia in Adults (2016 Edition), e.g., lifethreatening thrombocytopenia, major bleeding events (WHO Bleeding Score Grade 3 or 4) or the presence of symptoms or signs suggestive of potential bleeding, and should be confirmed by the sponsor. Patients who achieve a response (R) after receiving rescue treatment should be considered nonresponsive when calculated the response rate.

#### **Control Drug:**

Placebo

- Dose: Not applicable

- Method and route(s) of administration: The drug will be administered by subcutaneous injection once a week and 4 times per cycle, with no more than 3 cycles per subject in the overall trial.

#### Treatment Duration (for both phase 2 and phase 3 parts):

3 weeks, once a week, 4 doses.

If subjects who had a response (R) or complete response (CR) to study drug in the previous cycle during the 21-week follow-up period had relapse (platelets < 30 × 10 /L confirmed in 2 tests at least 1 day apart). Additional treatment cycle of study drug may be arranged once investigators considered as subjects were not indicated for rescue treatment and this should be confirmed by the sponsor. The treatment of the additional cycles continues with the original double-blind treatment, and the drugs are given once weekly for 4 weeks. The interval between the first dose of the additional cycles and the last dose of the previous cycle must be at least 4 weeks. The total number of the treatment cycles for subjects should not exceed 3, i.e. the total number of doses should not exceed 12.

#### Study Duration (for both phase 2 and phase 3 parts):

26 weeks in total (2-week screening + 3-week treatment + 21-week follow-up).

During the 21-week follow-up period, for subjects who receive additional treatment cycles, the subsequent visits after the first dose of additional cycles should be performed same as the visits from Day 0 (Visit 2) as specified in the study schedule. Except for randomization, all the procedures should be done. However, assessments to be performed should accord toVisit 20 in the study schedule. If the Week 24 visit is less than 5 weeks from the last dose of study drug, or the last treatment cycle has not been completed at the Week 24 visit, the follow-up period will be extended up to 5 weeks after the last study dose. For those subjects with extended follow-up period, the last visit assessments will also be performed as according to Visit 20 in the study schedule (see Flow Chart of Additional Treatment Cycles).

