#### Study Objectives:

Phase 2: Dose Selection and Efficacy Ev	valuation
Study Objectives:	Study Endpoints:
Primary Objectives	Primary Endpoints
- To evaluate the early efficacy of weekly subcutaneous HBM9161 340 mg and 680 mg treatment in patients with primary immune thrombocytopenia (ITP) to make a go/no go decision for the phase 3 part and select a dose to be further	
 
Proportion of subjects who achieve a response (R) during the period from Week 1 to Week 7.
 

studied in the phase 3 part, the the phase 3 part decision is go.	
Secondary Objectives	Secondary Endpoints

 
To assess the efficacy of weekly subcutaneous HBM9161 340 mg and 680 mg in patients with primary immune thrombocytopenia (ITP).
 
	
 
Proportion of subjects whose platelet count is ≥ 30 × 10^9/L and at least 2 times of baseline at 4 or more visits out of the 6 visits in the period of Week 19 through Week 24, and who had no bleeding events and no rescue treatment prior to those platelet counts
 

	
 
Proportion of subjects who achieve response (R) within 24 weeks
 

	
 
Proportion of subjects who achieve complete response (CR) within 7 weeks
 

	
 
Proportion of subjects who achieve complete response (CR) within 24 weeks
 

	
 
Proportion of subjects who achieve platelet count ≥ 50 × 10^9/L at least 2 times within 7 weeks
 

	
 
Proportion of subjects who achieve platelet counts ≥ 50 × 10^9/L at least 2 times within 24 weeks
 

	
 
Time to Response: time from imitation of treatment to first response (R) or complete response (CR)
 

	
 
Duration of response: time from response (R) or complete response (CR) to first unmet response (R) or complete response (CR)
 

	Note:
	- Reaction (R) is defined as:
	Platelet counts ≥ 30 × 10  /L and at least 2 times of baseline, confirmed by 2 tests (at least 7 days apart) , and no prior bleeding events and no rescue treatment.
	- Complete response (CR) is defined
	as: platelet counts ≥ 100 × 10  /L should be achieved and confirmed in at least 2 tests (at least 7 days apart) without prior bleeding events and no rescue treatment.

Safety Objective	Safety Endpoints

 
To assess the safety of weekly subcutaneous HBM9161 340 mg and 680 mg in ITP patients
 
	
 
Severity and incidence of adverse events during 24 Weeks
 

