Exploratory Objectives	Exploratory Endpoints

 
Other efficacy assessments
 
Biomarker assessments
 
Immunogenicity of HBM9161
 
Exploratory characteristics of the pharmacokinetics (PK) of HBM9161 in patients with primary immune thrombocytopenia based on population pharmacokinetic (PopPK) analysis
 
To assess the relationship between HBM9161 exposure and efficacy and adverse events
 
	
 
WHO bleeding score of subjects from baseline to Week 24
 
Change in platelet count over 24 weeks compared to baseline
 
Proportion of subjects with a decrease in ITP concomitant medication over 24 weeks compared to baseline
 
Proportion of subjects treated with rescue therapy within 24 weeks compared to baseline
 
Change in serum IgG, IgM, IgA, albumin levels from baseline to Week 24
 
Anti-platelet autoantibodies: to assess changes compared to baseline of anti-GPIIb/IIIa, anti-GPIb/IX, and anti-GPIa/IIa antibodies.
 
Anti-drug antibodies: to assess changes in serum anti-HBM9161 antibodies compared to predose.
 
Pharmacokinetics evaluation: all data of HBM9161 plasma concentration obtained in this study will be used for the PopPK analysis, which is to establish a PK model to characterize the PK of subcutaneous injection of HBM9161.
 
Dose-response assessment: to explore the correlation between PK/efficacy and PK/safety.
 

Phase 3: Efficacy and Safety Assessme	nt
Primary Objectives	Primary Endpoints

 
To evaluate the efficacy of weekly subcutaneous HBM9161 (dose to be determined) in patients with primary immune thrombocytopenia (ITP)
 
	
 
Proportion of subjects with ≥ 4 visits with platelet counts ≥ 30 × 10 /L and at least 2 times higher than baseline and no bleeding events and no rescue treatment in 6 visits from Week 19 to Week 24.
 

	,
	Note: The primary endpoint of Phase 3 may be reasonably changed based on the data available in Phase 2 to more accurately reflect the long-term efficacy of the product.
Secondary Objectives	Secondary Endpoints

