#### Statistical Analysis:

The primary endpoint in the phase 2 part is the proportion of subjects who achieve a response (R) between the Week 1 and Week 7. Based on data observed in this study and external information available, the sponsor will make following decisions based on the totality of information at the interim analysis at the end of Week 7 in the phase 2 part:

- whether to proceed to the phase 3 part;
- select a dose to befurther studied in the phase 3 part.

Whether to proceed to the phase 3 part will be based on the Go/No-Go decision framework. If at least one dose shows a high likelihood that the target efficacy can be achieved and the safety of this dose is acceptable, the phase 3 part will start. On the other hand, if the efficacy of both doses is shown to be unlikely to be clinically significant, the trial will be terminated and Phase 3 will not be initiated. If the analysis results do not meet any of the two situations above, the subjects will continue to be observed or sample size will be increased to collect more long-term efficacy data to decide whether to enter Phase 3. The dose selection for the Phase 3 will be based on the comparisons of the efficacy, safety and biomarkers between the two doses.

The primary efficacy endpoint in the Phase 2 is set primarily to verify the mechanism of action of the drug. Since the primary efficacy endpoint in the Phase 2 is for short-term efficacy assessment and the primary efficacy endpoint in the Phase 3 is for long-term efficacy assessment, the decision for Phase 3 will consider not only the observed short-term efficacy as measured by the Phase 2 primary efficacy endpoint, but also the long-term efficacy observed in subjects who have partially completed the trial, the predictions of

the long-term efficacy and the duration of efficacy based on the biomarkers, the efficacy and safety of the competitive products, and the safety data observed from this trial.

The primary endpoint of the Phase 3 is the proportion of subjects with a platelet count  $\ge 30 \times 10^{9}$ /L at  $\ge 4$  of 6 visits from Week 19 to 24 and the platelet count is at least twice baseline level, without bleeding events or rescue treatment. The statistical tests for differences in response rates between groups will be performed based on a normal approximation of the binomial distribution without continuity correction.

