## (continued)

Study Phase	Screen ing Phase	Tr	reatme	nt Pha	ase				Follo	w-up P	hase i				Early Withdraw al Visit b
Visit Number															ET
Weeks															
Days															
Visit Window (days)															
Review of Inclusion/Exclusion Criteria															
Subject Randomization															
Study Drug Administration															
Injection Site Assessment															Xp
Dispensing/Return of Subject Diary h															
Review of Subject Diary															
Adverse Event Collection															
WHO Bleeding Score															
Anti-HBM9161 Antibody Test i															
Immunoglobulins (IgG, IgM, IgA)												 		 	
Platelet Autoantibodies j															
PK Blood Sample Collection k															

Note:

a. Date of first dose of HBM9161 injection.

b. If the subject withdraws from the study early, the withdrawal visit should be completed within 2 days of the decision to withdraw from the study; if the subject withdraws in the middle of the treatment period, please observe the injection site reaction at the withdrawal visit until the reaction disappears.

c. The complete physical examination should be performed at the Screening Visit, Visit 6 (Week 4), Visit 9 (Week 7), Visit 20 (Week 24), and the Early Withdrawal Visit (Includes cardiovascular, respiratory, gastrointestinal, skin, neurological, and musculoskeletal systems, as well as head, eyes, ears, mouth, nose, throat, neck, lymph nodes and edema). Height and weight will be measured and recorded at the screening visit. Key physical examinations (including skin, mucosa and organ hemorrhage and edema) may be performed at other visits.

d. Viral serology test should be performed at screening, including HIV, HBsAg, HBcAb and HCV antibody. The HBV-DNA testing should also be performed in the subjects with HBsAg-negative but HBcAb-positive, and the subjects with clinically significant elevations in HBV-DNA are excluded.

e. The HBV-DNA testing is only performed in the subjects with HBsAg negative but HBcAb positive. The subjects with clinically significant elevations in HBV-DNA should be considered for the addition of the anti-HBV drugs according to the relevant guidelines.

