f. The subjects with the known tuberculosis infection, a high risk of tuberculosis infection, latent tuberculosis infection or a history of tuberculosis infection should be excluded. Other subjects should have a tuberculin test or interferon gamma release assay to rule out the active TB infection.

g. All the female subjects of childbearing potential should complete the blood human chorionic gonadotropin (HCG) pregnancy test at screening. The serum or urine pregnancy tests may be done at the subsequent visits.

h. The subject diary helps the subjects record the medications and the adverse event across the visits.

i. The ADA analysis will be performed under the control of the sponsor. The serum samples will be tested for anti-HBM 9161 antibodies using the currently approved bioanalytical methods. The raw data will be stored at the bioanalytical site. If the anti-HBM 9161 antibodies can be detected, the ADA titers will be further tested and further characterized using the validated cell-based NAb assays, if necessary, based on the ADA positive rate and titers.

j. Platelet autoantibodies, including anti-GPIb/IIIa, anti-GPIb/IX and anti-GPIa/IIa antibodies, will be detected by the monoclonal antibody-specific immobilization of platelet antigen (MAIPA) or enzyme-linked immunosorbent assay (ELISA) methods. From the start of the first dose of the additional cycles, the subsequent sampling will be performed according to the blood collection schedule from Day 0 (Visit 2) on the study schedule.

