## FLOW CHART OF ADDITIONAL TREATMENT CYCLES

Study Phase	Screening Phase	т	reatme	ent Ph	ase						Follov	v-up ph	ase					Adjustment Visits Caused by Additional Cycles									
Visit Number																											
Weeks																											
Days																											
Visit Window (days)																											
Visit Number for the Same Process																											
Visit Number for the Same Process																											
Visit Number for the Same Process																											
Visit Number for the Same Process																											
Visit Number for the Same Process																											
Visit Number for the Same Process																											
Visit Number for the Same Process																											
Visit Number for the Same Process																											
Visit Number for the Same Process																											
Visit Number for the Same Process																											
Visit Number for the Same Process																											
Visit Number for the Same Process																											
Visit Number for the Same Process																											
Visit Number for the Same Process																											
Visit Number for the Same Process																											
Visit Number for the Same Process																											
Visit Number for the Same Process																											
Visit Number for the Same Process																											

m.Initiation of the additional cycles per protocol requirements

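### Does re-treatment leave some subjects without the six Week 19 to 24 platelet counts that the Phase 3 primary endpoint needs?

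*Combined protocol and SAP*

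**What the plan says.** **Visits after re-treatment.** The Study Duration section, repeated in note l to the Study Schedule, says that "the subsequent visits after the first dose of additional cycles should be performed same as the visits from Day 0 (Visit 2"). Both places then turn to which procedures and assessments apply, give a rule for extending follow-up around the Week 24 visit, and send the reader to the Flow Chart of Additional Treatment Cycles. Note j says of autoantibody samples that "the subsequent sampling will be performed according to the blood collection schedule from Day 0 (Visit 2) on the study schedule".

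**The endpoint.** The Phase 3 primary endpoint in Study Objectives ends with "no rescue treatment in 6 visits from Week 19 to Week 24" and asks for at least 4 qualifying visits. The Statistical Analysis section repeats it as 4 or more "of 6 visits from Week 19 to 24 and the platelet count is at least twice baseline level". A Phase 2 secondary endpoint uses the same window: "at 4 or more visits out of the 6 visits in the period of Week 19 through Week 24".

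**Timing.** Note c to the Study Schedule gives the anchors "Visit 6 (Week 4), Visit 9 (Week 7), Visit 20 (Week 24"). Treatment Duration says: "The interval between the first dose of the additional cycles and the last dose of the previous cycle must be at least 4 weeks".

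**The flow chart.** It has screening, treatment and follow-up columns, a further block headed "Adjustment Visits Caused by Additional Cycles", and repeated rows that match visits to those following the same process. Its cells are blank in the text available here.

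**The concern.** The endpoint runs on calendar weeks, while the re-treatment sentence seems to reset the clock. The schedule is weekly at the start and at the end but sparser in between. If a reset subject follows only the restarted schedule, calendar Weeks 19 to 24 can fall in the sparse stretch, and fewer than four counts may be scheduled. A subject who regains and keeps a response after the second cycle could then fail the endpoint for want of visits rather than for low platelets. Only subjects who responded and then relapsed may be re-treated, so such losses would probably fall more on the active arm and bias the primary comparison against the drug.

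**Working it through.** **1. The plan's own figure.** Weeks 19 to 24 hold 24 − 19 + 1 = 6 weekly visits, which reproduces the stated six. With Visit 20 at Week 24, these are Visits 15 to 20.

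**2. The sparse stretch.** Visit 2 is Day 0 and Visit 9 is Week 7, so Visits 2 to 9 are weekly. That leaves Visits 10 to 14 (14 − 10 + 1 = 5 visits) for Weeks 8 to 18 (18 − 8 + 1 = 11 weeks).

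**3. Earliest restart.** The last dose of cycle 1 is on Day 21 (Week 3). Adding the 4-week minimum gives 3 + 4 = Week 7.

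**4. Counts if the restart replaces the calendar visits.** For a restart at week *w*, calendar Weeks 19 to 24 become restarted weeks (19 − *w*) to (24 − *w*). For *w* = 7 these are weeks 12 to 17; for *w* = 11, weeks 8 to 13. Assume a platelet count at every visit and Visits 10 to 14 at Weeks 9, 11, 13, 15 and 17. Neither assumption can be checked in the readable text.

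| One restart at week | Counts, Week 24 not kept | Counts, Week 24 kept |
|---|---|---|
| 7, 9, 11 | 3 | 3 |
| 8, 10, 12 | 3 | 4 |
| 13 | 4 | 4 |
| 14 | 4 | 5 |
| 15 | 5 | 5 |
| 16 | 5 | 6 |
| 17 or later | 6 | 6 |

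There are C(11,5) = 462 whole-week placements of the five visits. Some restart week falls below 4 counts in 462 of 462 if Week 24 is not kept, and in 442 of 462 if it is. Among the 141 placements with no gap above 3 weeks, the figures are 141 and 135. These are properties of possible schedules, not patient risks.

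**5. Counts if the calendar visits are kept.** Six, for every restart week. The whole question is therefore which premise the plan supports.

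**6. What the text supports.**

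- *The original clock continues.* The extension rule applies when the Week 24 visit falls less than 5 weeks after the last dose, or before the last cycle is complete. On a restarted clock, Week 24 is always 24 − 3 = 21 weeks after that cycle's last dose, so neither condition could arise. Week 24 must be calendar time. It is named because this rule needs it, which does not imply that Weeks 19 to 23 are dropped.
- *The neighbouring sentences concern content.* After the restart wording, both places say which procedures are done (all except randomization) and which visit's assessments apply. The restart sentence can be read as saying what is done from the first repeat dose onward. Nothing cancels a calendar visit.
- *The endpoint makes no exception.* All three statements of it require six visits in Weeks 19 to 24, whether or not a subject is re-treated.
- *The flow chart carries the detail.* Ordinary follow-up columns, rows matching visits by process, and a separate block for added visits suggest that calendar visits stay and take on the matching procedures. This is inference from the layout, not proof.

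**7. Who could be affected even on the adverse reading.** The fourth weekly count in the window comes at Week 22 at the earliest. A restart at week *w* means relapse within *w* − 3 weeks of cycle 1's last dose. Loss of an otherwise met endpoint needs response until 22 − (*w* + 3) = 19 − *w* weeks after cycle 2's last dose.

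| Restart week | Relapse within (weeks after cycle 1) | Response needed (weeks after cycle 2) |
|---|---|---|
| 7 | 4 | 12 |
| 8 | 5 | 11 |
| 9 | 6 | 10 |
| 10 | 7 | 9 |
| 11 | 8 | 8 |

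For restarts at Weeks 7 to 10, the second response must outlast the first. A subject who relapses again may receive a third cycle, and if it starts soon enough the weekly visits return: on the assumed spacing, restarts at Weeks 7 and 14 give 4 counts, or 5 with Week 24 kept.

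**The case for a change.** The strongest case for the concern is that sites may follow the prose, and the prose names only Week 24 on the calendar. With three scheduled counts, a requirement of four cannot be met however good the platelets are. With four, every one must qualify, while a subject who is not re-treated can miss two. Fixing the six counts by calendar week would take one sentence and about three blood counts per re-treated subject on the assumed spacing, so it could be argued that the sentence is worth adding whatever the chart shows.

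Two parts of this stand. The conditional arithmetic is correct, and the prose does not say in so many words that the Week 19 to 23 visits continue. The rest does not carry. Silence in the prose is not cancellation when the prose refers to a chart made for this purpose. If the chart keeps the visits, the extra sentence changes no count and no result. The harm also needs a week without a visit to be scored as a failure, which no readable text states. Any bias would run against the drug and would not inflate false-positive findings.

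**Conclusion.** The concern does not hold. The shortfall of 3 counts, or 3 to 4 with Week 24 kept, for a single restart at Weeks 7 to 12 follows only if the restarted visits replace the calendar visits and Visits 10 to 14 are spaced as assumed. The readable text does not establish the first condition: the Week 24 rule shows the original calendar still running, the endpoint requires six visits without exception, and the governing flow chart cannot be treated as silent because its cells were lost in extraction. With the calendar visits kept, every subject has six scheduled counts and the shortfall is zero. No effect on the trial's result can be computed in any case, since the documents give no re-treatment rate or timing. What remains is a point of reading: whether the chart's Week 19 to 23 columns stay in force for re-treated subjects, which the complete chart would settle. This conclusion rests on the readable prose and on the chart's headings and row labels; a complete chart that plainly dropped those visits would reopen the question.
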